9.5.2 GEM End (Study Period 1 End)

1. History review, assess for AEs since last visit
2. Perform clinical assessments
3. Download CGM data
4. Perform clinical assessments
5. Perform psychological assessments

6. Perform behavioral assessments
7. Complete Program Importance Scale
8. Collect blood for clinical laboratory tests, including proteomics
9. Place blinded CGM and activity monitor and instruct on how to mail back blinded CGM.

9.6 Visit 4/5- Study Period 2 Start

1. History review, assess for AEs since last visit
2. Blinded CGM data acquisition
3. Instruct participant on unblinded Freestyle Libre 2 CGM
 - a. Instruct on placement, use, strongly encourage scanning 20-40 times a day, but at a minimum scanning at least every 8 hours
 - b. Ensure participant account is working
 - c. Connect to study account
4. Instruct participant on activity monitor
 - a. Instruct on use
 - b. Reconfigure smartphone settings to unblind activity date
 - c. Verify participant account connection to study account
5. Review the GEM manual and read Unit 1 to ensure the participant understands the program. Encourage to complete 4 daily diary logs. Encourage significant other (if applicable) to also be present. Document whether significant other is present. To accommodate individual learning styles this may be done anytime within 1 week of the GEM Start Visit.
6. Set up text messaging (content, timing, frequency)
7. Schedule follow-up contact 2 weeks and 6 weeks later (when probability of dropout from lifestyle intervention peaks). Assess satisfaction with text messaging and change content/timing/frequency if necessary (and document).
8. Schedule Follow-up Visit for 4.5 months later (+/-2 weeks)
9. Schedule reminder contact for 2 weeks before next Visit; at that time, contact participant to assure they have a Libre 2 sensor inserted to collect the 14 days of end of study data.
10. Optional: For any participant coming off of the intervention, they will be asked at the end of the study visit 4 or 6, or contacted by email, phone, and/or letter to discuss if they would like to complete a short, semi-structured interview via audio and/or audio and video to provide feedback on the intervention to assist in improvements with the program for future studies. The interviews will be recorded and participants will be made aware of this. If any PHI is mentioned during the interview, it will be removed during the transcription process. This part is not required as part of the intervention and will not affect compensation or any study procedures.

9.7 Visit 5/6- Study Period 2 End

9.7.1 GEM End (Study Period 2 End)

10. History review, assess for AEs since last visit
11. Download CGM data
12. Perform clinical assessments
13. Perform psychological assessments
14. Perform behavioral assessments
15. Complete Program Importance Scale

16. Collect blood for clinical laboratory tests, including proteomics
17. Place blinded CGM and activity monitor and instruct on how to mail back blinded CGM.
18. Optional: For any participant coming off of the intervention, they will be asked at the end of the study visit 4 or 6, or contacted by email, phone, and/or letter to discuss if they would like to complete a short, semi-structured interview via audio and/or audio and video to provide feedback on the intervention to assist in improvements with the program for future studies. The interviews will be recorded and participants will be made aware of this. If any PHI is mentioned during the interview, it will be removed during the transcription process. This part is not required as part of the intervention and will not affect compensation or any study procedures.

9.5 Early Withdrawal Visit. A participant may withdraw from the study at any time and will be given the opportunity to meet with the PI if desired. Multiple attempts will be made to schedule the participant for an early withdrawal visit to perform assessments and review any AEs.

10 SAFETY EVENTS REPORTING AND DOCUMENTATION

10.1 Adverse Events. Adverse event means any untoward medical occurrence associated with the use of an intervention in humans, whether or not considered intervention-related (21 CFR 312.32 (a)). Adverse events will be recorded in the participant CRF. Adverse events will be described by duration (start and stop dates), severity, outcome, treatment and relation to study intervention, or if unrelated, the cause.

10.1.1 AE Severity. The National Cancer Institute’s Common Terminology Criteria for Adverse Events (CTCAE) Version 3.0 should be used to assess and grade AE severity, including laboratory abnormalities judged to be clinically significant. The modified criteria can be found in the study manual. If the experience is not covered in the modified criteria, the guidelines shown in Table 1 below should be used to grade severity. It should be pointed out that the term “severe” is a measure of intensity and that a severe AE is not necessarily serious.

10.1.2 Table 1. AE Severity Grading

Severity (Toxicity Grade)	Description
Mild (1)	Transient or mild discomfort; no limitation in activity; no medical intervention or therapy required. The subject may be aware of the sign or symptom but tolerates it reasonably well.
Moderate (2)	Mild to moderate limitation in activity, no or minimal medical intervention/therapy required.
Severe (3)	Marked limitation in activity, medical intervention/therapy required, hospitalizations possible.
Life-threatening (4)	The subject is at risk of death due to the adverse experience as it occurred. This does not refer to an experience that hypothetically might have caused death if it were more severe.

10.1.3 AE Relationship to Intervention. The relationship of an AE to the study intervention should be assessed using the following the guidelines in Table 2.

10.1.4 Table 2. AE Relationship to Study Intervention

Relationship	Comment
Definitely	There is clear evidence to suggest a causal relationship, and other possible contributing factors can be ruled out. The clinical event, including an abnormal laboratory test result, occurs in a plausible time relationship to study intervention administration and cannot be explained by concurrent disease or other drugs or chemicals.
Probably	There is evidence to suggest a causal relationship, and the influence of other factors is unlikely. The clinical event, including an abnormal laboratory test result, occurs within a reasonable time after administration of the study intervention, is unlikely to be attributed to concurrent disease or other drugs or chemicals.
Possibly	There is some evidence to suggest a causal relationship (e.g., the event occurred within a reasonable time after administration of the trial medication). However, other factors may have contributed to the event (e.g., the participant's clinical condition, other concomitant events). Although an AE may rate only as "possibly related" soon after discovery, it can be flagged as requiring more information and later be upgraded to "probably related" or "definitely related", as appropriate.
Unlikely to be related	A clinical event, including an abnormal laboratory test result, whose temporal relationship to study intervention administration makes a causal relationship improbable (e.g., the event did not occur within a reasonable time after administration of the study intervention) and in which other drugs or chemicals or underlying disease provides plausible explanations (e.g., the participant's clinical condition, other concomitant treatments).
Not related	The AE is completely independent of study intervention administration, and/or evidence exists that the event is definitely related to another etiology. There must be an alternative, definitive etiology documented by the clinician.

10.2 Serious Adverse Events (SAE)

An SAE is defined as any AE that results in any of the following outcomes:

- death
- a life-threatening adverse experience
- inpatient hospitalization or prolongation of existing hospitalization
- a persistent or significant disability/incapacity
- a congenital anomaly/birth defect

Other important medical events may also be considered an SAE when, based on appropriate medical judgment, they jeopardize the subject or require intervention to prevent one of the outcomes listed.

10.2.1 Serious Adverse Experience Reporting

Study site will document all SAEs that occur (whether or not related to study intervention) per local requirements. Any urgent reporting will be done within the acceptable parameters and timeline to all necessary reporting agencies. The collection period for all SAEs will begin after informed consent is obtained and end after procedures for the final study

visit have been completed. In accordance with the standard operating procedures and policies of the local Institutional Review Board (IRB)/Independent Ethics Committee (IEC), the site investigator will report SAEs to the IRB/IEC.

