Description of Study Intervention	Blinded CGM data (obtained through the use of the Libre Pro) and blinded activity data (obtained through the use of a FitBit) will be obtained for 2 weeks on all participants at the start and end of the study, and baseline clinical data collection and psychosocial scales will be completed prior to randomization. The intervention group will be given Libre 2 supplies for 4 months, an activity monitor, and the 4-chapter GEM paper guide. The intervention group will complete a virtual or inperson study visit where they will receive instructions on how to apply their unblinded Freestyle Libre and connect it to the study account, as well as how to

	
register their Fitbit to the study account. If the visit will be conducted remotely, participants will be mailed their CGM, Fitbit, and the GEM manual. Participants will receive one telephone call to review use of the GEM Guide and call at two weeks and six weeks later when the probability of dropouts from lifestyle intervention peaks. Participants will follow the self-directed GEM guide for 4 months (a 1-month treatment period followed by a 3-month maintenance period) while wearing a FitBit activity monitor and a Freestyle Libre 2 CGM. Participants will be given this guide and a study email so they can easily ask questions about the GEM program during treatment. Fielding GEM questions will help the study progress smoothly and will gain information that might improve the Guide in the future. Relevant questions and corresponding answers will be posted on a study website for all participants to review, if desired. However, all medical management questions will be referred back to the participant's treating physician. The GEM Guide for Prediabetes contains the following information in four chapters: Glucose Impact of Routine Choices, Recovering from BG Excursions, Reducing BG Excursions, and Maintenance. The RC group will follow recommendations from their primary care physicians and clinicians that will be tracked for later analysis. RC participants will have the opportunity to receive the intervention four months after consenting and completing of the RC pre-post assessments. Comprehensive proteomics analysis will be done at the same time after all samples have been collected.

Study Duration	
This study will last approximately 24 months from the beginning of subject recruitment to data analysis.

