5.2.4 Safety Endpoints

- Frequency of adverse events

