9.4 Visit 2/3– Start

9.4.1 RC Start (for participants randomized to RC), at least and as close as practical to 14 days following Secondary Baseline visit

1. History review, assess for AEs since last visit
2. Notify participant of randomization to RC
3. Blinded CGM data acquisition
4. Collect activity monitor
5. Schedule Follow Up visit for 4.5 months later (+/-2 weeks)
6. Schedule reminder contact for 2 weeks before next Visit; during contact, ask about interest in GEM if eligible

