9.5 Visit 3/4 – Study Period 1 End

9.5.1 RC End (All subjects)

1. History review, assess for AEs since last visit
2. Give participant blinded CGM sensor and activity monitor and instruction for returning devices via mail if not doing GEM.
3. Perform clinical assessments
4. Perform psychological assessments
5. Perform behavioral assessments
6. Collect blood for clinical laboratory tests, including proteomics
7. Assess interest/appropriateness of crossing over to GEM
 - a. If crossing over to GEM, proceed to schedule visit 5 once A1c is confirmed via phone call.
 - b. If not crossing over to GEM, participation complete once CGMs returned via mail.

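### SAE collection is stated to end with the final-visit procedures, but the end-of-study blinded sensor is worn for about 14 days after that visit with no later contact to ask about events

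*Combined protocol and SAP*

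**What the plan says.** Section 10.2.1 sets the SAE window: "The collection period for all SAEs will begin after informed consent is obtained and end after procedures for the final study". The rest of the sentence makes the end point the completion of that visit's procedures.

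The last visit on each path starts a new period of device wear:

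- RC End (section 9.5.1): "Give participant blinded CGM sensor and activity monitor and instruction for returning devices via mail if not doing GEM".
- GEM End, period 1 (section 9.5.2): "Place blinded CGM and activity monitor and instruct on how to mail back blinded CGM". Section 9.7.1 repeats this step at the end of period 2 for participants who crossed over.

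The Protocol Summary gives the length of wear: blinded sensor and activity data "will be obtained for 2 weeks on all participants at the start and end of the study". Appendix 1 marks these end visits both for blinded sensor placement and as the final visit or study end (for RC End, only when the participant does not go on to GEM).

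Two other places bear on when observation ends. Section 9.5.1 says "If not crossing over to GEM, participation complete once CGMs returned via mail". Section 8.7 says that adverse event information is gathered over the whole study. The only safety endpoint, in section 5.2.4, is "Frequency of adverse events".

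**The concern.** Read plainly, section 10.2.1 closes SAE collection on the day of the last visit, while a protocol-required device wear is only beginning. Each scheduled event check looks back to the previous visit, so a check after the wear is needed to cover it. The baseline wear has one, because the Start visit follows about 14 days later: "RC Start (for participants randomized to RC), at least and as close as practical to 14 days following Secondary Baseline visit". The final wear has none. After the last visit the documents describe only the return of devices by mail and an optional feedback interview, for which no adverse-event question is specified.

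An event in that fortnight, such as a skin reaction at the sensor site or an unrelated hospital admission, might never be recorded. The wear is also when the post-assessment data for the primary endpoint are collected, so it is a core study procedure. What is at stake is the completeness of the safety endpoint and a clear rule for study staff. The efficacy comparison is not affected.

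**Working it through.** The plan states no exposure share, so there is no figure to reproduce. The check counts days after the last event check on each path.

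**Inputs**

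- Blinded wear: 14 days at the start and 14 at the end (Protocol Summary). Section 9.5.1 gives no length for the RC End wear, so 14 is the planned value.
- Start visit: 14 days after baseline, plus or minus 2 (Appendix 1).
- End visit: 4.5 months after Start (sections 9.4.1 and 9.4.2). With a month of 365.25/12 days, this is 4.5 × 30.44 = 137 days.
- Libre 2 supply for GEM: 4 months (Protocol Summary) or 4.5 months (section 5.1), that is 122 or 137 days.
- Crossover among RC: 50% anticipated; section 5.1 reports that less than 50% were in fact available.
- Eligibility is assumed to be confirmed at Visit 1, so that consent and baseline coincide.

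**Which final wears are followed by an event check**

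| Path | Wear after the visit | Later check |
|---|---|---|
| RC, no crossover | after RC End | none |
| RC, crossover | after RC End | Visit 4/5, step 1 (section 9.6) |
| RC, crossover | after period 2 GEM End | none |
| Randomised to GEM | after period 1 GEM End | none |

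Every path ends with one uncovered wear of about 14 days.

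**Share of calendar follow-up**

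- RC non-crossover and randomised GEM: 14 / (14 + 137 + 14) = 14/165 = 8.5%.
- RC crossover, both periods: 14 / (14 + 137 + 14 + 137 + 14) = 14/316 = 4.4%.

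**Share of study-sensor wear**

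- RC non-crossover: 14 / (14 + 14) = 50%. With a baseline wear of 12 or 16 days: 14/26 = 54% or 14/30 = 47%.
- Randomised GEM: 14 / (14 + 122 + 14) = 14/150 = 9.3%, or 14 / (14 + 137 + 14) = 14/165 = 8.5%.
- RC crossover, both periods: 14/164 = 8.5% or 14/179 = 7.8%.
- Whole RC arm, RC-period wear, with crossover share c: (1 − c) × 14/28. This is 25% at c = 0.50, 37.5% at an assumed c = 0.25, and 50% only at c = 0.

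**The case against.** The strongest reply is that the documents can be read so that no gap exists. The cut-off quoted above governs SAEs only. Section 8.7 has adverse events gathered over the whole study, and section 9.5.1 ends participation of RC non-crossovers only when the sensor comes back. Placing the sensor and explaining its return are listed visit procedures, so completing them might be taken to include the wear. This stands in part: the adverse event window is ambiguous rather than plainly closed. But section 10.2.1 does not say that the wear is included, and on either reading no contact is described at which events would be collected.

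A reader might also infer that half of the RC arm's device exposure lies outside safety follow-up. The documents do not support that. Crossovers' RC-end wear is checked at Visit 4/5, so the 50% belongs to non-crossovers alone.

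A reader might further set 50% for RC against 8% for GEM and infer a loss that differs by arm and biases adverse event frequency. That contrast mostly reflects the choice of denominator. SAEs are documented whether or not they are related to the intervention, so time under observation is the relevant base, and there the gap is 8.5% for RC non-crossovers and GEM alike. Within period 1 the difference actually runs the other way: at 50% crossover an RC participant has on average 0.5 × 14 = 7 unchecked days, against 14 for GEM. Section 11 describes no between-arm test of adverse events.

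Finally, the consequence is small. The protocol rates the trial as minimal risk and the use of the Libre 2 as non-significant risk. This stands, and it limits the weight of the point.

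**Conclusion.** The point holds as a minor gap in safety follow-up. On the plain reading of section 10.2.1, SAE collection ends about 14 days before the last required sensor wear does. On any reading, no event check follows that wear for GEM completers, RC non-crossovers or period 2 completers. Sections 8.7, 9.5.1 and 10.2.1 give different end points and need to be reconciled.

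The best single measure of size is 8.5% of calendar follow-up for GEM and RC non-crossovers. The 50% figure is correct only for the sensor wear of RC non-crossovers; for RC-period wear across the arm it is 25% at the anticipated crossover, and more if fewer cross over. A material bias between arms is not shown, and the number of missed events cannot be estimated because the documents give no event rate. The sizes rest on a planned 14-day final wear, the scheduled visit times, and eligibility confirmed at Visit 1.

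**What to change.** State one end point in sections 8.7, 9.5.1 and 10.2.1: AE and SAE collection runs from consent to the end of the last study sensor wear, or to return of the devices. Apply it to all three final visits (RC End without crossover, GEM End in period 1, GEM End in period 2). Then provide the means to collect: one adverse-event question in the mail-back materials, or a brief contact when the devices are returned. Add the matching entry to Appendix 1.

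The cost is a sentence of protocol text and one question or short contact per participant. It is a small addition rather than a free one, because the documents describe no existing return form and no reminder after the last visit; the scheduled reminders come two weeks before a visit.

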10.3 Protocol Defined Events of Interest Requiring Real-Time Reporting

This study poses no greater than minimal risk and real-time reporting is not necessary.

10.4 Study Discontinuation

10.4.1 Early Discontinuation of Study Intervention

A subject may be discontinued from study treatment at any time if the subject or the investigator feels that it is not in the subject's best interest to continue. The following is a list of possible reasons for study treatment discontinuation:

- Subject withdrawal of consent (or assent)
- Subject is not compliant with study procedures
- Adverse event that in the opinion of the investigator would be in the best interest of the subject to discontinue study treatment
- Protocol violation requiring discontinuation of study treatment
- Lost to follow-up
- Pregnancy

If a subject is withdrawn from treatment due to an adverse event, the subject will be directed to obtain treatment, if necessary, by their primary care provider until the abnormal parameter or symptom has resolved or stabilized.

All subjects who discontinue study treatment should be offered an early discontinuation visit as soon as possible and then should be encouraged to complete all remaining scheduled visits and procedures.

All subjects are free to withdraw from participation at any time, for any reason, specified or unspecified, and without prejudice.

Reasonable attempts will be made by the investigator to provide a reason for subject withdrawals. The reason for the subject's withdrawal from the study will be specified in the subject's source documents. Refer to study evaluations for early termination procedures.

10.4.2 Withdrawal of Subjects from the Study

A subject may be withdrawn from the study at any time if the subject or the investigator feels that it is not in the subject's best interest to continue.

All subjects are free to withdraw from participation at any time, for any reason, specified or unspecified, and without prejudice.

Reasonable attempts will be made by the investigator to provide a reason for subject withdrawals. The reason for the subject's withdrawal from the study will be specified in the subject's source documents. As noted above, subjects who discontinue study treatment early (i.e., they withdraw prior to the follow-up visit) should be offered an early discontinuation visit. Refer to Section 10 for early termination procedures.

10.4.3 Replacement of Subjects

Subjects who withdraw from the study will not be replaced.

10.5 Protocol Deviations

A protocol deviation is defined as any change, deviation, or departure from the study design or procedures of a research project that is NOT approved by the institution's IRB prior to its initiation or implementation, OR deviation from standard operating procedures, Good Clinical Practices (GCPs), federal, state or local regulations. These protocol violations may be major or minor violations.

The PI will use continuous vigilance to identify and report deviations.

When a protocol violation occurs, it will be discussed with the investigator and a Protocol Violation Form detailing the violation will be generated. This form will be signed by the Investigator. A copy of the form will be filed in the site's regulatory binder.

11 STATISTICAL METHODS AND CONSIDERATIONS

The primary analyses will be a 2 (group) X 1 (change pre to post assessment) analysis of covariance analyzing change variables, with baseline variables serving as co-variants. The Benjamini-Hochberg procedure³¹ will be employed to control for multiple comparisons. Exploratory correlational analyses will be performed to determine significance of baseline and change variable relationship to primary outcome variable. Analyses will be conducted in SAS v. 9.4. Statistical analysis of de-identified data will be completed at the University of Virginia. The University of Virginia has done all statistical analysis for previous GEM studies.

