Primary Objective	To determine if individuals with prediabetes can use GEM plus Libre CGM to improve metabolic control.

Primary Endpoints	Pre-post reduction in percentage of CGM readings > 120 from blinded pre-post LibrePro; additional outcomes of particular interest include, A1C and BG variability
Secondary Objectives	
 (1) To determine if individuals with prediabetes can use the GEM manual with Libre CGM to improve other clinical, psychosocial, and behavioral outcomes. (2) To explore psychological (readiness to change) and physiological (proteomics) measures. (3) To generate user feedback about improving the intervention.
Secondary Endpoints	
 (1) Endpoints will include psychosocial scales, basic demographic information, comparative labs, Steps, Hours Active, or Active Minutes. (2) Analysis of individual proteins and protein pathways measured through use of a multiplex proteomics platform. (3) Endpoint will include the Program Importance Questionnaire
Participation Criteria	
Inclusion Criteria:
 
 • Age 25-70 years • A1C 6.0-6.4 • Documented diagnosis of prediabetes • Have a smart phone • Able to read English, as the GEM guide is currently only available in English • Willing and able to follow the study procedures as instructed 
Exclusion Criteria:
 
 • Diagnosis of diabetes mellitus • Currently taking any diabetes medication • Currently taking medication that promotes insulin resistance or otherwise interferes with metabolic control (e.g. prednisone) • Has a condition that precludes a low carbohydrate diet, such as gastroparesis • Has a physical or medical condition that precludes walking 120 steps per minute, for 10 minutes or longer • Has documented kidney disease that would preclude participation in study per PI discretion • Active or planned cancer treatment. • Extreme visual or hearing impairment that would impair ability to use real-time CGM • Pregnant or anticipates becoming pregnant in the next 4 months. • Anticipates moving within the next 4 months. • Treating physician, for any reason, considers their patient inappropriate for the study (e.g. uncontrolled bipolar disease)
Sample Size	Up to 70 screened participants with prediabetes and an A1c between 6.0-6.4 to provide a cohort of 36 enrolling in the trial, with a goal of at least 30 participants completing the trial.

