More investigation needs to be done to establish the importance of CGM in treating prediabetes. Yost et al's investigation of CGM and low carbohydrate diets of adults with prediabetes²⁰ suggested that CGM plus a low carbohydrate diet was acceptable to their sample, led to lower A1c, and reduced sense of vulnerability to developing diabetes. However, it had multiple limitations that will be addressed by our proposed study: briefly, the aforementioned article 1) only had 20 days of CGM, 2) did not have a routine care group to distinguish the effects of diagnosis and enrollment in a study on A1c, AUC, weight reduction, etc., 3) did not measure A1c before and after their intervention, 4) required three face-to-face and two telephone patient contacts, 5) employed a primary outcome that was satisfaction with CGM and low carbohydrate diets, and 6) had a subject sample that was narrow, requiring a BMI of >30. In addition, our study will include the combination of the GEM manual and CGM to actively teach subjects how to interpret, predict, and effect the CGM results which is hypothesized to be a more active and powerful behavioral modification.

Our proposed investigation addresses many of the aforementioned limitations by focusing on reducing AUC rather than weight or CGM time above 180. Thus, GEM targets reducing post prandial, as well as periodic post snack and drink, glucose excursions. Our approach would employ two groups (with no weight restriction) to identify the effects of participation in a study. Our primary outcome variable of reduction in AUC (reduced % CGM readings above 120) is more appropriate to our patient sample. GEM requires no face-to-face visits. In contrast to the above studies that use

CGM to educate either the patient or artificial intelligence, GEM uses CGM feedback to educate, motivate, activate, and investigate. Additionally, our proposed study will also allow us to explore two preliminary issues: [name] has developed the Treatment Optimization Scale that is intended to predict which patients are more likely to do better on medication or lifestyle intervention. We anticipate that individuals with a strong preference to actively engage in a lifestyle intervention will do better on CGM and in the GEM group. Additionally, we will begin to explore proteomics in the study population, as described below.

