5.2.2 Primary Endpoint

- pre-post reduction in percentage of CGM readings >120, from blinded pre-post LibrePro.

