11.1 Data Sets Analyzed

- All randomized subjects will be included in analysis

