11.4 Analysis of Secondary Endpoints

Secondary outcome variables will be analyzed with standardized statistical methods for each variable type used to evaluate individual proteins and protein pathways. Correlations will be examined comparing data obtained from proteomic analyses, clinical measurements, and glucose excursion parameters. Data from participants will be compared to themselves to identify changes as a function of glucose control. Data will also be analyzed for groups of individuals by comparing the means and standard errors of the mean.

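### The planned correlations with the primary change score adjust for neither arm nor the outcome's own baseline, so some can be significant by construction, and none can separate response to GEM from prognosis

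*Combined protocol and SAP*

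**What the plan says.** Section 5.2.2 defines the primary endpoint as "pre-post reduction in percentage of CGM readings >120, from blinded pre-post LibrePro", which is a change score. Section 11 plans the group comparison as an "analysis of covariance analyzing change variables, with baseline variables serving as co-variants" and then adds: "Exploratory correlational analyses will be performed to determine significance of baseline and change variable relationship to primary outcome variable". Section 11.1 gives one analysis set: "All randomized subjects will be included in analysis". Section 11.4 adds a second family: "Correlations will be examined comparing data obtained from proteomic analyses", set against clinical measurements and glucose excursion parameters. On multiplicity, section 11 says: "The Benjamini-Hochberg procedure³¹ will be employed to control for multiple comparisons".

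Section 3.2 states an expectation about who benefits: "We anticipate that individuals with a strong preference to actively engage in a lifestyle intervention will do better on CGM and in the GEM group". This refers to the Treatment Optimization Scale.

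Four things are not stated for the correlations: whether arms are pooled or arm is adjusted for; whether baseline % >120 is a tested correlate or an adjustment variable; whether a crossover participant's two change scores both enter; and whether any arm-by-predictor term will be fitted. The baseline adjustment in the ANCOVA is not extended to them.

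**The concern.** A correlation test assumes that the correlation is zero when nothing is going on. Two of the planned types need not meet that assumption.

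- **Coupling.** Baseline % >120 is part of its own change. Measurement error that raises the baseline also raises the apparent reduction, so the two correlate even if no participant is more responsive than another. Another baseline metric from the same trace, such as glucose variability, carries some of the same error.
- **Arm mixing.** If GEM shifts two change variables and the arms are pooled, the group difference appears as a correlation even if the variables are unrelated within each arm. The Protocol Summary expects GEM to improve % >120, BMI, depressive symptoms and empowerment together, so the condition is plausible.

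A third problem is one of interpretation. A scale that correlates with change may mark people who would have improved in either arm. Only a difference between arms in that relationship supports a claim about response to GEM.

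The trial hopes to tell responders from non-responders and to inform a larger study. A spurious predictor or change-change link could be carried forward into that work.

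**Working it through.** **Inputs from the documents.** The outcome is a pre-post change (section 5.2.2). The Protocol Summary plans "to provide a cohort of 36 enrolling in the trial, with a goal of at least 30 participants completing the trial". Allocation was 2:1 (RC:GEM) and then changed to 1:1 (section 5.1). No effect size, SD, pre-post correlation or alpha is given, so there is no stated figure to reproduce.

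**Assumptions.** Two-sided 0.05; pre-post correlation r from 0.5 to 0.9; treatment shift d from 0 to 1.5 within-arm SDs on both change variables; equal pre and post variances. Rejection rates come from 40,000 simulated trials per cell (20,000 for the regression models).

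**1. Coupling.** Let pre = T + e1 and post = T + e2, each with variance 1, and corr(pre, post) = r.

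- cov(pre, pre − post) = 1 − r
- SD(pre − post) = √(2(1 − r))
- corr(pre, pre − post) = (1 − r)/√(2(1 − r)) = √((1 − r)/2)

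For example, r = 0.7 gives √(0.3/2) = 0.39. The sign is negative if change is coded post − pre. With 30 participants, |r| above 0.361 is significant.

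| Assumed r | Expected correlation | Significant, n=30 | Significant, n=36 |
|---|---|---|---|
| 0.5 | 0.50 | 83% | 90% |
| 0.7 | 0.39 | 58% | 67% |
| 0.9 | 0.22 | 22% | 26% |

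A different baseline metric from the same trace, correlated 0.5 to 0.9 with baseline % >120 (assumed), is significant in 9% to 72% of trials at n=30. A baseline variable unrelated to baseline % >120 stays at 5%.

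**2. Arm mixing.** Take two change variables that are independent within arm, both shifted by d, with a fraction p on GEM. The pooled correlation is p(1 − p)d² / (1 + p(1 − p)d²). With p = 0.5 and d = 1.0 this is 0.25/1.25 = 0.20; with d = 1.5 it is 0.5625/1.5625 = 0.36.

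| Assumed d | 15 GEM / 15 RC | 10 GEM / 20 RC | 18 / 18 |
|---|---|---|---|
| 0 | 5% | 5% | 5% |
| 0.5 | 6% | 6% | 7% |
| 0.8 | 11% | 10% | 13% |
| 1.0 | 19% | 16% | 22% |
| 1.5 | 54% | 47% | 63% |

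An unrelated baseline variable stays at 5% at every d, because randomization makes baseline independent of arm.

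**3. Do the remedies work?**

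- Change-change correlation adjusted for arm: 4.8–5.1%.
- Arm-by-baseline interaction in a model for post: 4.9–5.1%.
- Same-trace baseline metric adjusted for arm and baseline % >120: 5.0–5.2%.
- Own baseline against its change, adjusted for arm only (n=30): still 81%, 57% and 22% at r = 0.5, 0.7 and 0.9. Arm adjustment alone does not remove coupling.

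**The case against.** The best defence is that these analyses are labelled exploratory, in a study the protocol calls a pilot and a feasibility study, and that no decision rests on them. That limits the consequence. It does not repair the test: the plan still says significance will be determined, and Benjamini-Hochberg handles many tests, not a correlation that is non-zero by construction.

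The defence also stands against several stronger readings that a reader might infer.

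- **That any baseline correlate of change is an artefact.** Under the model above, change is made up only of the two errors. A variable related just to the stable level T has zero expected correlation with it. Coupling needs shared measurement error.
- **That a Treatment Optimization Scale finding would be a coupling or arm-mixing artefact.** It is a baseline questionnaire, and nothing in the documents ties it to sensor error. The problem there is solely prognosis versus response, and the figures above do not size it.
- **That the plan pools the arms.** It does not say so. Section 11.1 defines only who is analysed, and section 11.4 also describes within-participant comparisons. The arm-mixing rates are conditional on pooling, and at d of 0.5 or less they are negligible.
- **That baseline % >120 will certainly be tested.** Section 11 refers to baseline variables in general and does not name it.

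It is also fair to say that interactions with about 15 per arm will be imprecise and that simpler devices exist. Oldham's method (correlating change with the pre/post mean) keeps 4.8–5.1% for own baseline, and arm adjustment suffices for arm mixing. Each covers only its own part, and neither addresses prognosis versus response.

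**Conclusion.** The concern holds in a limited form. As written, the correlations can produce artefacts in two places: own baseline or same-trace metrics against the change in % >120 (22% to 83% for own baseline at n=30, over assumed r from 0.9 to 0.5), and change-change pairs if arms are pooled (6% to 54% with 15 per arm, over assumed d from 0.5 to 1.5). All of these rates rest on assumed r, d and alpha, because the documents give none. Demographics and other baseline variables that do not share the sensor error keep a 5% rate.

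The prognosis-versus-response point needs no numerical assumption: section 3.2 expects preference to matter in the GEM group, and no planned analysis compares the relationship between arms.

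A reader might take this as a threat to the main result. It is not one: the primary between-group analysis does not use these correlations. The change should be made because it is nearly free and uses data already being collected.

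**What to change.** In sections 11 and 11.4, replace the raw correlations with the following:

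- For each baseline predictor, regress post % >120 on baseline % >120, arm and the predictor. For the Treatment Optimization Scale and other candidate predictors of response, add arm × predictor. Read the main effect as prognosis and rest any claim about response on the interaction.
- For change-change and proteomic associations, use arm-adjusted or within-arm partial correlations, also adjusted for the relevant baselines.
- Do not test baseline % >120 against its own change by raw correlation.
- Do not enter a crossover participant's two change scores as independent observations.
- Report estimates with confidence intervals, labelled exploratory.

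The cost is a few sentences in the plan and no new data. The downside is wide intervals for the interactions, which is what a trial of this size can honestly offer.
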